## **Data Acquisition and Maintenance**

Data will be collected using REDCap (Research Electronic Data Capture) electronic data capture tools hosted at Rush University. REDCap is a secure, web-based software platform designed to support data capture for research studies. REDCap provides 1) an intuitive interface for validated data capture; 2) audit trails for tracking data manipulation and export procedures; 3) automated export procedures for seamless data downloads to common statistical packages; and 4) procedures for data integration and interoperability with external sources.

The PI will be responsible for maintaining the security of the data stored both in REDCap and on the secure network server. Data will only be identified with the study ID of the participant. The codes that link the name of the participant and the study ID will be kept confidential by the PI on a secure network drive, with permissions set on an as needed basis. All data will be stored on the Department of Preventive Medicine's MS SQL server relational database. Rush data network security and availability on DMC servers is supported by Rush Information Services servers. Rush University has two data centers on our Chicago campus at [name] and [name] All servers are located in the locked data centers, with access limited to authorized personnel via a biometrics access system. Data centers each have SinorixTM 227 and Ecaro-25TM Clean Agent Chemical Fire Suppression Systems, redundant backup diesel generator and uninterruptible power supply (UPS) systems, and redundant chillers for cooling.

The Rush data network is segmented and protected from the internet by a Palo Alto Networks® firewall. Access to the network from the internet requires multi-factor authentication. All network users are required to have a unique login and password. The passwords must be changed every 180 days and must be complex (i.e., must have: a capital letter, small letter, number, special character, and be at least 8 characters in length). Change management policies and procedures are in place to protect the integrity of the systems. A Change Management Review Board meets once each week to review all proposed software and hardware changes. Systems are backed-up nightly and the data is duplicated and sent to an offsite storage facility.

### **Monitoring of Data Quality**

We will embed data validation checks within each questionnaire (i.e., required items, allowable ranges of response values) to ensure valid data is entered by participants at the time of data collection. Study staff will complete a verification process for each questionnaire record before 'locking' the record to prevent further changes. Only the PI will have administrative privileges to unlock completed records. Our study database will also include a scheduling program that tracks when research contacts occur and when visits or calls need to be scheduled based on the participants' condition.

### **Monitoring of Safety Data**

Overall framework. The PI will be responsible for monitoring the safety and efficacy of the project, executing the Data and Safety Monitoring (DSM) plan, and complying with the reporting requirements. She will be assisted by [name] (study Co-Investigator), a board-certified Internal Medicine physician and Medical Director of the Rush University Prevention Center. The PI will provide a summary of the DSM report to NHLBI on an annual basis as part of the progress report. The DSM report will include the participants' sociodemographic characteristics, expected versus actual recruitment rates, retention rates across all study assessments, any quality assurance or regulatory issues that occurred during the past year, summary of Adverse Events (AEs) and Serious Adverse Events (SAEs), and any actions or changes with respect to the protocol. The DSM report to NHLBI will also include, when available, the results of any data analyses conducted. No interim analyses of the data are planned.

The PI will ensure the project is conducted according to the protocol. She will oversee data quality checks on a regular basis to ensure completeness and accuracy of ongoing data collection. Through weekly meetings with project staff, the PI will discuss issues related to progression of the project and factors that may

affect outcome including review of data quality and security, recruitment, and retention. The PI will be available for meetings with project staff outside the weekly allotted time to discuss any issues that may arise, including AEs or unanticipated problems. The PI will ensure all project staff have completed research ethics training as required by the IRB and are thoroughly trained on study procedures.

Adverse events. Adverse events are defined as any untoward or unfavorable medical occurrence in a human subject, including any abnormal sign (e.g., abnormal physical exam or laboratory finding), symptom, or disease, temporally associated with the subject's participation in the research, whether or not considered related to the subject's participation in the research. At all assessment points (i.e., Days 0, 28, 42, 56, and 120), we will monitor participant reports of adverse events related to: 1) nicotine withdrawal symptoms; 2) COPD symptoms, including COPD exacerbation, defined as an acute worsening of symptoms of COPD requiring new or increased doses of systemic corticosteroids, antibiotics, and/or emergency treatment or hospitalization; 3) utilization of outside study treatment (e.g., smoking cessation, mental health services, pulmonary rehabilitation, and medication use); and 4) any other symptoms participants believe may be related to study participation. Procedures for identifying and reviewing adverse events, including SAEs, are as follows: The research assistant will review each assessment to identify symptoms of moderate or greater severity, indicated by 1) Minnesota Tobacco Withdrawal Scale score > 24, 2) COPD Assessment Test score > 20, 3) any report of acute COPD exacerbation since the prior assessment, and/ or 4) any other symptom identified by participants to be of moderate or greater severity. In all cases of an assessment indicating symptoms of moderate or greater severity, an assessment summary will be emailed to the PI and study Co-I [name] within 24 hours. Drs. [name] and [name] will review the assessment summary and respond within 24 hours to advise on appropriate actions to be taken. Actions may include continuing to monitor symptoms, contacting the participant for further assessment, advising that the participant contacts his or her healthcare provider, or advising that the participant presents to the Emergency Room.

Serious adverse events. A serious adverse event is defined as follows: death, a life-threatening adverse event, inpatient hospitalization or prolongation of existing hospitalization, a persistent or significant disability/incapacity, a congenital anomaly/birth defect, or a medically significant event that may require medical or surgical intervention. Risks of participation will be continually monitored and appropriate measures implemented in cases of unforeseen adverse events. If a serious adverse event occurs, the study PI will notify the IRB and the appropriate NHLBI program official. These events will be reported regardless of whether they appear to be related to study procedures. A summary of the SAEs that occurred during the previous year will be included in the annual progress report to NHLBI and the IRB Continuing Review.

Unanticipated problems. All unanticipated problems will be reported to the PI and study Co-I [name] within 24 hours by research staff. The PI will notify the Rush University IRB and the appropriate NHLBI program official within five (5) business days of discovering any unanticipated problems involving risks to participants and others.

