#### Measures.

Psychological Factors. Anhedonia will be assessed with the Environmental Reward Observation Scale (EROS), which measures amount of pleasure experienced from daily activities. Anxiety sensitivity will be assessed with the Anxiety Sensitivity Index (ASI-3), a measure of tendency to fear body sensations. Distress intolerance will be assessed with the Distress Tolerance Scale (DTS), which assesses perceived tolerance of negative physical or emotional states.

Smoking-Related Variables. We will administer a Smoking History Questionnaire to assess baseline smoking characteristics. We will administer validated PROMIS measures of nicotine dependence and smoking coping expectancies. We will administer the Cessation Fatigue Scale, a measure of perceived tiredness of

trying to quit smoking. Smoking status will be assessed with timeline follow-back methods, and will be supplemented with an assessment of expired carbon monoxide (CO) at inperson assessment sessions to provide bioverification of smoking status. Lastly, an outside-study treatment review will be conducted to identify any pharmacotherapy or behavioral therapy for smoking cessation received outside of the study.

COPD-Related Variables. We will conduct a chart review to identify participants' most recent sixminute walk test and spirometry (FEV1) values prior to COPD hospitalization. The chart review will also be used to supplement participants' self-report of any hospitalization for COPD at the time of the 3-month follow-up assessment. COPD symptom impact will be assessed with the COPD assessment test (CAT), an 8-item questionnaire measuring the global impact of dyspnea on health status. PROMIS measures will be used to assess task avoidance and emotional response to dyspnea symptoms.

Table 2. Phase 2 Study Measures	idy Measures Timepoint Assesse		
,	Baseline	Treatment Sessions	End-of- treatment
Demographic Questionnaire	X		
Contact Form	X		
Psychological Factors			
Anxiety Sensitivity Index	X		X
Environmental Reward Observation Scale	X		X
Distress Tolerance Scale	X		X
Smoking-Related Measures			
Smoking Motives Questionnaire-Revised	X		
Smoking History Questionnaire	X		
PROMIS-Nicotine Dependence	X		X
PROMIS-Coping Expectancies	X		X
Cessation Fatigue Scale	X		X
Smoking timeline follow-back	X		X
CO assessment	X	X	X
Outside-study treatment review	X	X	X

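### Adverse events outside withdrawal, COPD and outside treatment are collected only if the participant thinks them study-related, so reportable non-COPD hospitalizations and deaths can be missed

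*Combined protocol and SAP*

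**What the plan says.** Section 15.0, Monitoring of Safety Data, sets two broad standards. An adverse event is any unfavorable medical occurrence associated in time with participation, "whether or not considered related to the subject's participation in the research". Serious adverse events include death and inpatient hospitalization of any kind, and the rule for them is: "These events will be reported regardless of whether they appear to be related to study procedures".

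The collection rule in the same section reads: "At all assessment points (i.e., Days 0, 28, 42, 56, and 120), we will monitor participant reports of adverse events related to" four things:

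1. nicotine withdrawal;
2. COPD symptoms, with exacerbation taken to mean "an acute worsening of symptoms of COPD requiring new or increased doses of systemic corticosteroids, antibiotics, and/or emergency treatment or hospitalization";
3. care received outside the study, with mental health services and medication among the examples;
4. "any other symptoms participants believe may be related to study participation".

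The section then gives one procedure for finding and reviewing adverse events and says that it includes the serious ones. A research assistant checks each assessment for any of four signals: a withdrawal score above 24, a COPD Assessment Test score above 20, a COPD exacerbation since the last assessment, or another symptom that the participant rates as moderate or worse. A case with any of these goes to the PI and a co-investigator within 24 hours.

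A second source appears in Section 4.0 (Phase 2, Measures, COPD-Related Variables): a chart review to "supplement participants' self-report of any hospitalization for COPD at the time of the 3-month follow-up assessment".

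**The concern.** The definition and the reporting duty both exclude relatedness as a criterion. The residual collection item brings it back and leaves the judgement to the participant. An admission that the participant regards as having nothing to do with a smoking study is still a reportable serious event, but the plan does not ask about it.

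At stake is the completeness of the annual summary of adverse and serious adverse events that goes to NHLBI, and of the serious-event summary in the IRB continuing review. Section 15.0 states that no Data Safety Monitoring Board will be convened, so oversight rests with the PI in coordination with the IRB. Their summaries can be no more complete than the collection behind them.

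**Working it through.** The plan gives no event rate or expected count, so there is no figure to reproduce. The check is to take three kinds of serious event and trace each through every route described.

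| Event | Four elicited categories | Four review signals | Chart review |
|---|---|---|---|
| COPD hospitalization | Yes, category 2 | Yes, as an exacerbation | Yes, at 3 months |
| Non-COPD hospitalization that the participant sees as unrelated | Not 1, 2 or 4; category 3 may pick up related care or new medication | Only if the participant names a symptom of at least moderate severity | Not covered |
| Death | None; it cannot be self-reported | None; they need a completed assessment | Not mentioned |

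Four further steps:

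- **Where hospitalization appears.** In the collection and review text, hospitalization and emergency treatment occur only inside the definition of COPD exacerbation. Section 15.0 states no all-cause question.
- **What category 3 adds.** It has no relatedness filter, and its list is illustrative. It could reveal some non-COPD care. General inpatient admission is not among its examples, however, and use of outside treatment is not one of the four review signals.
- **Timing.** The listed assessment days are 0, 28, 42, 56 and 120. The intervals are 28, 14, 14 and 120 − 56 = 64 days. In the last interval no assessment is listed, so an event early in it depends on recall at Day 120 or on informal contact.
- **Other monitoring text.** Monitoring of Data Quality describes a scheduling program that tracks contacts and calls due. The serious-event paragraph promises continual monitoring of risk. Neither says what is done, for safety purposes, when an assessment is missed. Section 15.0 makes the pilot fully remote, by phone or online, so staff would not learn of an event through an in-person visit.

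The first row is well covered. The second and third are reportable under the plan's own rule, but no stated step is designed to find them.

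**The case against.** The strongest reply is that the plan catches more than its fourth category suggests. The fourth review signal has no relatedness filter. A participant who mentions a cardiac symptom of moderate severity is referred to two investigators within 24 hours, whatever its cause. Category 3 names mental health services and medication use, so a psychiatric admission could well surface there. A missed contact would show in the scheduling program and could come up at the weekly staff meetings, where retention is discussed. This stands as partial cover. It means that a reader who infers that no flag could ever fire, or that a psychiatric admission would go unseen, goes beyond the text. It does not supply a prompt: each route depends on the participant raising a symptom or on staff noticing something informally.

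A second reply is that the Phase 3 assessment forms cannot be read here. The chart review sits under the Phase 2 measures, and no Phase 3 measures table is given. The withdrawal scale used in Section 15.0 is missing from the Phase 2 table, so Phase 3 evidently has instruments that are not shown. This also stands, and it limits the point to what is described. The mention of a 3-month follow-up does suggest that the chart review is meant for the pilot trial, because Phase 2 participation ends about one week after the quit date.

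A third reply is that this is a single-site behavioral pilot that the IRB has designated minimal risk. That bears on how serious the gap is. It does not remove the mismatch between the collection rule and the reporting rule.

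**Conclusion.** The concern holds as a mismatch between the stated collection rule and the plan's own definitions. A non-COPD hospitalization can go unreported, and no way of learning of a death is described. It is worth correcting before or during the pilot trial, but it does not threaten the efficacy analysis. The conclusion assumes that Section 15.0 describes Phase 3 safety collection in full; an unshown form with an all-cause question would narrow it.

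Three stronger readings are not supported:

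- **That the summaries would omit these events.** Only can be missed is justified, given the partial routes above.
- **That a number of missed events can be given.** Full follow-up of 62 participants for 120 days is 62 × 120 / 365 = 20.4 person-years. The documents give neither an admission rate nor the non-COPD share. Any assumed all-cause rate would also count COPD admissions, which are already elicited.
- **That event counts would be distorted between arms.** Nine weekly sessions against mailed materials makes this conceivable, but the plan describes no comparison of adverse events by arm, and nothing in it shows that attribution would differ.

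**What to change.** Bring the collection text in Section 15.0 into line with its own adverse event definition and serious-event rule:

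1. Replace the fourth category with a neutral question, asked at each assessment in both arms: any hospitalization, or any new or worsened symptom, since the last assessment, whatever the cause.
2. Add any reported hospitalization to the review signals. Emergency visits as such are not a serious-event criterion in Section 15.0, so flagging all of them is not needed to close this gap.
3. Widen the 3-month chart review from COPD hospitalization to all-cause hospitalization and death, and state that it applies to Phase 3. Note its limit: Section 7.0 also recruits through community organizations, and admissions elsewhere may not appear in the site's records.
4. Have the existing scheduling program treat a missed assessment as a prompt for a status check, and state how a death would then be established.

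The cost is a change of protocol wording, a small change to the REDCap assessment, more unrelated events to log and somewhat more chart-review work. Treatment, endpoints and sample size are unchanged.

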## 1.0 Purpose of the Study:

Chronic Obstructive Pulmonary Disease (COPD) is caused primarily by smoking and smoking cessation is the first-line treatment for slowing disease progression. Despite this, nearly 50% of COPD patients continue to smoke following diagnosis. Smokers with COPD report high rates of co-occurring conditions – nicotine dependence, depression, and anxiety – which serve as barriers to quitting. The proposed research will develop and pilot test a behavioral intervention designed to target the common psychological factors underlying these co-occurring conditions and foster smoking cessation among COPD patients. Specific aims are:

Aim 1: Refine behavioral treatment components. We will conduct a series of semi-structured qualitative interviews with COPD providers (pulmonologists, nurses, and respiratory therapists) that will elicit feedback on key elements of treatment design (components, methods, and milestones) and implementation (safety, tolerability, and acceptability) to guide treatment tailoring and foster engagement.

Aim 2: Develop a multi-component behavioral treatment to address psychological risk factors among COPD patients. We will conduct a component analysis using single case design experiments with 15 participants to a) examine the contribution of each treatment component to the behavioral target of smoking for affect regulation, and b) establish proof-of-concept on the clinical endpoint of initial cessation ( $\geq$ 24 hours abstinence). Hypothesis: Behavioral treatment components will produce a) clinically significant reductions in smoking for affect regulation ( $\geq$  30%), and b) achievement of initial cessation in  $\geq$  60% of participants.

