Aim 3: Examine effects of psychological risk factor reduction on smoking outcome. Informed by Aim 2, we will conduct a pilot trial in which 62 participants are randomized to the multi-component behavioral treatment (9 weekly sessions) or self-guided treatment (mailing of printed self-help materials). Each participant will make a quit attempt at week 4. The primary outcome is number of days abstinent for 2 weeks post-quit (range = 0-14 days); secondary outcomes are smoking status at 3 months post-quit, COPD functioning, activity avoidance, and depression and anxiety symptoms. **Hypothesis**: Participants in the behavioral treatment vs. self-guided treatment will demonstrate a) greater number of abstinent days, and b) longer latency to smoke during the quit attempt.

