Component 1: Mindfulness. This module introduces mindfulness training skills, with the goal of cultivating nonjudgmental, present-focused experience of emotions, thoughts, and physical sensations related to cigarette smoking. By progressing though a series of experiential exercises (e.g., awareness of the breath, anchoring in the present), this module seeks to reduce maladaptive attempts to control negative emotions and facilitate tolerance of the physical and emotional symptoms of nicotine withdrawal.

Component 2: Interoceptive Exposure (Practice Quitting). This module introduces interoceptive exposure, a technique in which participants purposefully and systematically complete exercises to evoke physical sensations typically associated with anxiety and distress, in order to reduce fear and avoidance of these sensations. Interoceptive exercises will focus on a gradual exposure to nicotine withdrawal symptoms, through a series of 'practice quit attempts' (i.e., brief periods of smoking abstinence without intention to permanently quit).

Component 3: Behavioral Activation (Countering Emotional Behaviors). Lastly, this module introduces behavioral activation, which seeks to increase positive emotions by systematically introducing greater

engagement with natural rewards. Treatment sessions focus on the identification of avoidance strategies, including cigarette smoking as a coping strategy for negative emotions. The goal of this treatment module is to replace smoking with adaptive coping strategies to facilitate contact with and enjoyment of reinforcing activities that are incompatible with smoking.

Treatment Fidelity. All treatment sessions will be delivered by trained study counselors, supervised by the PI, a licensed clinical psychologist. [name] has extensive experience in cognitive-behavioral therapy for mood and anxiety disorders, as well as behavioral counseling for smoking cessation. She obtained specialized training in delivery of the proposed intervention at the Unified Protocol Institute at Boston University in October, 2017. Sessions will be audio recorded, with 20% of sessions reviewed by an independent evaluator using standardized fidelity ratings for each UP module.

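### The Phase 3 safety escalation rule has score cut-offs for withdrawal and COPD impact but none for depression or anxiety, so a non-serious moderate or severe mood score that nobody raises may go unescalated

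*Combined protocol and SAP*

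**What the plan says.** The adverse events paragraph of section 15.0 sets the rule for the pilot trial. "The research assistant will review each assessment to identify symptoms of moderate or greater severity", and the paragraph lists what counts: "1) Minnesota Tobacco Withdrawal Scale score > 24, 2) COPD Assessment Test score > 20, 3) any report of acute COPD exacerbation" since the previous assessment, and/or, fourth, "any other symptom identified by participants to be of moderate or greater severity". Any of these leads to an emailed summary to the PI and Co-I within 24 hours, and they respond within a further 24 hours. Assessments are on Days 0, 28, 42, 56 and 120.

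Section 1.0, Aim 3, states that "secondary outcomes are smoking status at 3 months post-quit, COPD functioning, activity avoidance, and depression and anxiety symptoms". It also says: "Each participant will make a quit attempt at week 4". The same section notes that smokers with COPD "report high rates of co-occurring conditions", and names depression and anxiety among them.

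Section 4.0 (Procedures to Minimize Risk) has the PI respond to distress or worsening mental health and arrange psychiatric referral. It does not say how a worsened questionnaire score would come to the PI's notice.

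**The concern.** The rule gives the research assistant a number to act on for withdrawal and for COPD impact. For mood it gives none, although the trial measures depression and anxiety in people who often have both and who are all asked to quit smoking. A research assistant who follows the list as written could see a severe depression score and have no listed reason to send it on, unless the participant had also named the symptom. The PI's undertaking to respond is only useful if the information arrives.

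The list also matters because section 15.0 makes the pilot fully remote, which leaves staff fewer chances to notice a change for themselves. The participants at stake are those with a non-serious but moderate or severe mood score that no one mentions.

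**Working it through.** The plan has no figure to reproduce here. The check is a reading of the trigger list against the rest of the document, followed by a simple ceiling on workload.

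**Step 1. Classify the triggers (section 15.0, adverse events).**

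| Trigger | Type | Uses a depression or anxiety score? |
|---|---|---|
| Withdrawal scale > 24 | Score | No |
| COPD Assessment Test > 20 | Score | No |
| Acute COPD exacerbation | Event | No |
| Other symptom, participant-identified | Judgement | Not stated |

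There are 4 triggers: 2 score cut-offs, 1 event and 1 participant-identified. Mood cut-offs number 0 of 2 here, and none appears elsewhere in the document. Mood is not a named adverse event domain either; mental health enters that paragraph only through use of outside services.

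**Step 2. Put one case through the rule.** Take a participant with a severe depression score, a withdrawal score of 24 or less, a COPD Assessment Test score of 20 or less, no exacerbation, no serious event and no symptom volunteered. The first three triggers do not fire. The fourth depends on whether answering a questionnaire counts as identifying a symptom. If it does not, no summary is sent. If it does, the research assistant still has no stated score at which mood becomes moderate.

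**Step 3. Check the other routes.**

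- *Withdrawal score.* The Mindfulness component aims to "facilitate tolerance of the physical and emotional symptoms of nicotine withdrawal", and section 10.0 lists withdrawal-related distress as a risk. The withdrawal score may therefore pick up some mood change, but it is not a measure of depression or anxiety.
- *Staff consultation.* Section 4.0 and the weekly meetings in section 15.0 allow staff to raise a problem with the PI. This requires someone to have noticed it.
- *Serious adverse events.* These are reported whatever their cause, but only if serious.

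These routes leave the case in Step 2 uncovered when neither the participant nor staff raise it.

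**Step 4. How often could it arise?** The quit attempt at week 4 falls at about 4 × 7 = Day 28. Days 42, 56 and 120 are then 42 − 28 = 14, 56 − 28 = 28 and 120 − 28 = 92 days later, so 3 of the 5 assessments are clearly post-quit. Which of the 5 collect mood scores is not shown. The Phase 2 measures table has PROMIS depression and anxiety short forms at baseline and end of treatment, but no Phase 3 table is available. The number of unescalated scores therefore cannot be estimated.

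A ceiling on the review load can be given. Assume all 62 participants attend all 5 assessments, with one depression and one anxiety score at each: 62 × 5 = 310 assessments, and 310 × 2 = 620 scores. This bounds the checking and does not predict the number of flags.

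**The case against.** The strongest reply is that this is a matter of monitoring intensity in a study that the IRB designated minimal risk, with a behavioral intervention only. The existing cut-offs follow the participants' disease and the withdrawal risk named in section 10.0. Being a secondary outcome does not make a measure a safety signal: activity avoidance is also on that list and has no cut-off. A mood questionnaire answer can reasonably be read as a participant-identified symptom. Staff are to be thoroughly trained and meet the PI weekly, and the PI is a licensed clinical psychologist.

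Much of this stands. It makes the gap narrow, and secondary-outcome status alone would not justify a trigger. But the minimal-risk designation does not explain why mood is left to interpretation while withdrawal and COPD impact are given numbers, in a trial whose own rationale stresses depression and anxiety.

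Three stronger readings are tempting and are not supported:

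- A reader might infer that worsening mood has no safety coverage. It has partial coverage through the four routes above.
- A reader might infer that the plan breaks its own commitment. Section 4.0 promises a response by the PI; it does not promise screening of scores.
- A reader might point to the interval between Day 56 and Day 120 as evidence of missed worsening. No assessment is listed in that interval, so a score trigger could not act there before Day 120. That concerns assessment spacing, not the missing cut-off.

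**Conclusion.** The concern holds in a limited form. The escalation list has no explicit rule for depression or anxiety scores, and whether a moderate or severe one is passed on depends on how the research assistant reads the fourth trigger. The exposed cases are non-serious ones that neither the participant nor staff raise. Their number is unknown and may be small.

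This is a cheap safety improvement worth making before Phase 3 enrolment. It does not show that the monitoring plan is unsound.

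The conclusion assumes that mood measures are collected at one or more of the five listed assessments, as Aim 3 implies, and that the trigger list is applied as written. The instrument and schedule for Phase 3 could change how often the gap arises, but not the absence of a rule in the text available.

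**What to change.** Add a fifth trigger to the adverse events paragraph of section 15.0: at every Phase 3 assessment where the depression or anxiety measure is collected, including Day 0 if given then, any score in that instrument's published moderate-or-greater range. This matches the severity standard the paragraph already uses. Write the cut-off for each measure into the protocol before Phase 3 enrolment; the documents supply no value, so the PI and Co-I must enter it. Route it through the existing 24-hour email.

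An absolute level is enough. The two existing score triggers work that way, and a change-from-baseline rule would need a further threshold and stored earlier values.

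The cost is a short protocol change and two more scores to check per assessment, at most 620 under the full-attendance assumption above. No new data collection is needed, since the trigger applies only where mood is already measured. Summaries may be frequent, because depression and anxiety are common in this population and a persistently moderate score would be flagged each time. Continued monitoring is already among the permitted responses, so a flag need not lead to further contact.
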